## 11 DATA ANALYSIS

### 11.1 Primary Endpoint and Sample Size Determination

The primary objective of this study is to quantify the dose-response relationship between oral vadadustat once daily dosing for 6 weeks and change in Hb in Japanese subjects with NDD-CKD in order to define the starting dose for use in Phase 3 clinical studies in Japan.

Change in Hb is defined as the Hb measured at the EOT visit minus the mean pre-treatment Hb. Pre-treatment Hb is defined as the average of 2 Hb values obtained prior to treatment based on the qualifying screening Hb value and the Hb value at the baseline visit. Linear regression analysis will be used to calculate the relationship between vadadustat dose and change in Hb.

The target enrollment will be approximately 48 subjects for the study with 12 subjects enrolled in each of the 4 treatment groups.

Based on the results from Study AKB-6548-CI-0005 that was conducted in the United States and evaluated vadadustat in patients with anemia secondary to NDD CKD, it is reasonable to assume that the expected mean Hb changes from baseline to Week 6 will be 0, 0.5, 0.7, and 1.2 g/dL for the placebo, 150 mg, 300 mg, and 600 mg vadadustat dose groups, respectively, with a common standard deviation of 0.68 g/dL among the 4 treatment groups. With these assumptions, the study will have >85% power to detect a non-zero slope in a dose-response relationship using linear regression analysis and  $\alpha=0.05$ , based on simulation of 10,000 repetitions using SAS® software, Version Number 9.4.

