Statistical Considerations	
The primary analysis will use a linear regression analysis to quantify the association between vadadustat dose and mean change in Hb (ie, to assess the vadadustat dose-response relationship). Comparison of each vadadustat dose group versus baseline will be performed. All tests of significance will be performed using a 0.05 two-sided significance level.
 
The target enrollment will be approximately 48 subjects for the study with 12 subjects enrolled in each of the 4 treatment groups. Based on the results from Study AKB-6548-CI-0005 that was conducted in the United States and evaluated vadadustat in patients with anemia secondary to NDD-CKD, the expected mean Hb changes from baseline to Week 6 will be 0, 0.5, 0.7, and 1.2 g/dL for the placebo, 150 mg, 300 mg, and 600 mg vadadustat dose groups, respectively, with a common standard deviation of 0.68 g/dL among the 4 treatment groups. With these assumptions, the study will have >85% power to detect a non-zero slope in a dose-response relationship using linear regression analysis and <math>\alpha=0.05</math>, based on simulation of 10,000 repetitions using SAS® software, Version Number 9.4.

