### 5.1 Primary Objective and Endpoint

The primary objective of this study is to assess the dose-response relationship between oral vadadustat once daily dosing for 6 weeks and the change in Hb in Japanese subjects with anemia secondary to NDD-CKD; in order to define the starting dose for use in Phase 3 clinical studies in Japan.

The primary endpoint that will be used to assess this objective is the mean change in Hb levels from pre-treatment to the end of the primary efficacy period (Week 6).

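### The straight-line primary model does not fit the protocol's own planning means at the low dose, and the only other stated per-dose inference leaves out the placebo arm

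*Protocol*

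**What the plan says.** The Protocol Synopsis (Statistical Considerations) sets the primary analysis as a "linear regression analysis to quantify the association between vadadustat dose and mean change in Hb". Section 11.1 says much the same: "Linear regression analysis will be used to calculate the relationship between vadadustat dose and change in Hb". That wording comes from the preceding version in the file, because Section 11 of the latest version is not in the part shown. Section 5.1 gives the purpose of the dose-response assessment: "in order to define the starting dose for use in Phase 3 clinical studies in Japan".

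The synopsis also states what the sponsor expects to see: "the expected mean Hb changes from baseline to Week 6 will be 0, 0.5, 0.7, and 1.2 g/dL". These four values belong to placebo and the three active doses in rising order. Each group is planned with 12 subjects, and one SD, 0.68 g/dL, is assumed throughout. The claim of more than 85% power is for a non-zero slope.

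Beside the regression, the synopsis plans a comparison of each vadadustat group with baseline. Section 11.5 of the preceding version adds descriptive summaries and box plots by treatment group. The text shown names no comparison of a dose with placebo, no non-linear model and no check of fit.

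**The concern.** Rejecting a zero slope shows that Hb response rises with dose. It does not say how large the effect is at each dose, and that is what a choice among doses needs.

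The expected means do not lie on a line. They rise by 0.5 over the first 150 mg, by 0.2 over the next 150 mg and by 0.5 over the last 300 mg. About 42% of the full effect (0.5/1.2) is expected at a quarter of the top dose, where a line through the origin would put 25%. A single slope spreads that early rise across the whole range, so it pulls the low-dose effect down.

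The other stated inference does not repair this. A within-group change from baseline includes any drift, regression to the mean or placebo response. The randomized placebo group, which exists to remove these, enters stated inference only as one point on the line.

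**Working it through.** **Inputs** (all from the Synopsis, Statistical Considerations): doses 0, 150, 300, 600 mg; mean changes 0, 0.5, 0.7, 1.2 g/dL; SD 0.68; 12 per group; two-sided alpha 0.05. Assumption: the regressor is randomized dose in mg.

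**The line under the planning means.** Mean dose is 262.5 and mean response 0.60.
- Sum of squares of dose: 12 × (262.5² + 112.5² + 37.5² + 337.5²) = 12 × 196,875 = 2,362,500.
- Cross-products per subject set: −112.5×0.5 + 37.5×0.7 + 337.5×1.2 = 375.
- Slope = 375/196,875 = 0.001905 g/dL per mg. Intercept = 0.60 − 0.001905×262.5 = 0.10.

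**The protocol's own figure.** Noncentrality = 0.001905 × √2,362,500 / 0.68 = 4.31. With 46 df this gives 98.8% power. Simulation gave 98.8% (100,000 repetitions) and 98.6% (10,000). The claim of more than 85% holds, with a wide margin.

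**Line against planning means** (coverage of nominal 95% intervals, 100,000 simulated trials):

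| Dose | Planned | Slope × dose (effect over placebo) | Coverage | Fitted change (intercept + slope × dose) | Coverage |
|---|---|---|---|---|---|
| 150 mg | 0.50 | 0.286 | 12% | 0.386 | 83% |
| 300 mg | 0.70 | 0.571 | 85% | 0.671 | 94% |
| 600 mg | 1.20 | 1.143 | 95% | 1.243 | 94% |

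At placebo the line fits a rise of 0.10 where none is planned.

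**Detail at 150 mg, effect over placebo.**
- Line: SE = 150 × 0.68/√2,362,500 = 0.066. Expected limits are 0.286 ± 2.013×0.066, about 0.15 to 0.42. The bias of 0.214 is about 3.2 standard errors, which explains the 12%.
- Direct contrast: SE = 0.68 × √(2/12) = 0.278. Expected limits on 44 df are about −0.06 to 1.06.
- Root mean square error: line √(0.214² + 0.066²) = 0.22; direct contrast 0.28.

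**Detail at 150 mg, change from pre-treatment.**
- Line: SE = 0.68 × √(1/48 + 112.5²/2,362,500) = 0.110. Expected limits are about 0.16 to 0.61, which include 0.50.
- Root mean square error: line √(0.114² + 0.110²) = 0.16; group mean 0.68/√12 = 0.20.

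**Would the data reveal the misfit?** The residuals of the planning means from the line are −0.100, 0.114, 0.029 and −0.043. The lack-of-fit noncentrality is 12 × 0.0257/0.68² = 0.67, so the 2-df F test has about 10% power.

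**Sensitivity.** If dose were coded as levels 0, 1, 2, 3, the slope would be 0.38 per level and the intercept 0.03. At 150 mg this gives 0.38 over placebo and 0.41 fitted change. The understatement shrinks but remains.

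**The case against.** The strongest reply is that the protocol uses the regression for one hypothesis, a non-zero slope, and nowhere says that dose-specific effects will be read as slope times dose. This is correct. A reader might infer that the plan will report 0.29 g/dL as the 150 mg effect, but the documents do not support that. On the stated endpoint, change from pre-treatment, the fitted value is 0.39, with limits that include 0.50.

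A reader might also infer that the line's confidence limits are miscalculated. They are not. The standard error is right for the slope, and the undercoverage comes from bias. Under the same means the line has the smaller root mean square error at 150 mg on both scales, so the direct contrast is not the more precise estimator.

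It is also tempting to say that the starting-dose decision turns on the 150 mg estimate. Section 5.1 links the dose-response to the starting dose but gives no rule, and safety, PK and target attainment are collected as well.

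The planning means are sample-size assumptions taken from a US study, not known truth. The misfit in the fitted mean (0.11) is smaller than the standard error of a 12-subject group mean (0.20).

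Finally, Section 11 of the latest version and the SAP were not available, and either may contain placebo contrasts. For that reason the point is confined to what the synopsis fixes: a straight line used to quantify the relationship, means that do not follow one, and a per-dose comparison with baseline instead of placebo. Descriptive group means would let a reader subtract placebo by eye, but without a stated interval.

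**Conclusion.** The point holds as a moderate one that is cheap to correct. If the planning means are true, a straight line in mg understates the 150 mg effect over placebo by 0.21 g/dL (0.29 against 0.50, about 12% coverage) and the 150 mg change from pre-treatment by 0.11 g/dL (0.39 against 0.50, about 83% coverage). At 300 mg the effect over placebo is understated by 0.13 g/dL, with 85% coverage; at 600 mg the line does well. The only other dose-specific inference in the text shown leaves out the randomized control.

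These sizes rest on the planning means, an SD of 0.68, 12 evaluable subjects per group and randomized dose in mg as the regressor. The primary slope test is sound and amply powered, so the trial's main hypothesis is not in question.

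**What to change.** Keep the slope test as the primary hypothesis test. Replace or supplement the comparison of each dose group with baseline by dose-specific differences from placebo with 95% confidence intervals, from a model with dose as a four-level factor adjusted for pre-treatment Hb. State that these estimates will be reported beside the fitted line and will inform the starting-dose conclusion. Any lack-of-fit test should be labelled descriptive: at about 10% power, a non-significant result would not support linearity.

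The cost is one extra model, with no added subjects or visits. The intervals will be wide: SE about 0.28 g/dL per contrast before covariate adjustment, against 0.066 for the line at 150 mg. Under the planning means the 150 mg interval would run from about −0.06 to 1.06, so the contrasts serve estimation and will not by themselves settle the dose.

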### 11.5 Efficacy and PD Analyses

The entire set of efficacy outcomes will be defined in the statistical analysis plan (SAP). In addition to the primary endpoint analysis defined above, the following efficacy endpoints will also be assessed:

- Actual values and change (absolute and percent) from baseline in Hb, HCT, RBC count, and reticulocyte count (both absolute and percent)
- Actual values and change (absolute and percent) from baseline in iron, TIBC, TSAT, ferritin (both absolute and percent), and hepcidin

For purposes of analysis, a pre-treatment average (defined as the average of 2 samples obtained prior to treatment [ie, the qualifying screening value and baseline value]) will be used as the baseline value for Hb and RBC count, and last observation before the first dose of study medication will be used as baseline for other parameters.

Changes from baseline of efficacy and PD parameters will be summarized using descriptive statistics by treatment groups and each scheduled assessment, and results will be displayed using box plots.

Linear regression analysis will be performed for Hb change from baseline to Week 6, to assess the vadadustat dose-response relationship. Similar analysis will be performed for change from baseline to Week 6 of reticulocyte count (both absolute and percent), hematocrit, and RBC count.

Also, similar linear regression analysis will be performed for change from baseline to Week 6 of the iron indices (ie, iron, TIBC, ferritin, and TSAT) and hepcidin will be evaluated.

All tests of significance will be performed using a 0.05 two-sided significance level.

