### **7.4.2 Rescreening**

Subjects who fail to meet the qualifying criteria for Hb or eGFR during screening may be considered for rescreening at the discretion of the investigator, if it is felt that the subject's status has changed and that the subject may now qualify for the study. Additionally, subjects who fail to qualify for the study based on low ferritin, TSAT, folate, or B12 values may be considered for rescreening after receiving replacement therapy.

If intravenous (IV) iron is used to replete iron stores, the last dose of IV iron must be administered at least 4 weeks prior to rescreening.

Screening is limited to 3 attempts (during the initial screening and 2 additional rescreening attempts). Subjects who fail to qualify for the study at the initial screening visit will receive a new subject number for each rescreening attempt. If rescreened, the subject will also sign a new informed consent form and will repeat all screening procedures for each rescreening attempt.

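### The only dose-level comparison the protocol names is each vadadustat dose against its own baseline; no dose-versus-placebo contrast is specified

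*Protocol*

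**What the plan says.** Synopsis, Statistical Considerations: "The primary analysis will use a linear regression analysis to quantify the association between vadadustat dose and mean change in Hb". The next sentence is "Comparison of each vadadustat dose group versus baseline will be performed", followed by "All tests of significance will be performed using a 0.05 two-sided significance level". The same sequence stands in all three protocol versions in the file.

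The sample size text in the same place plans "approximately 48 subjects for the study with 12 subjects enrolled in each of the 4 treatment groups", with expected mean changes of "0, 0.5, 0.7, and 1.2 g/dL for the placebo, 150 mg, 300 mg, and 600 mg vadadustat dose groups, respectively" and a "common standard deviation of 0.68 g/dL among the 4 treatment groups".

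Section 11.5 adds regressions of other parameters on dose and descriptive material: "Changes from baseline of efficacy and PD parameters will be summarized using descriptive statistics by treatment groups and each scheduled assessment". It names no contrast of a single dose with placebo. Section 11 can be read only in the two earlier versions, because the latest breaks off within Section 8.1.4.

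On entry and baseline, Section 7.2 requires screening Hb of 10.5 g/dL or less. Section 7.4.1 allows one retest of a failing laboratory value. Section 7.4.2 says that subjects failing on iron, folate or B12 "may be considered for rescreening after receiving replacement therapy". Pre-treatment Hb is the mean of the qualifying screening value and the Day 1 value.

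**The concern.** The objective is to describe the dose-response relationship and so define a starting dose for Phase 3. A positive slope shows that response rises with dose. It does not by itself show what 150 mg or 300 mg achieves over no treatment. The only comparison named at that level has no control. The sentence on the significance level follows directly. Section 6.3 also reports a paired test of baseline against Week 6 for the earlier study on which the design is modelled. A within-group significance test is therefore the natural reading.

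Such a test attributes every cause of change to the drug. Subjects enter because a screening Hb was low, and that selected value makes up half of the pre-treatment average. Some upward movement is therefore plausible on any treatment. A dose could look active against baseline with no effect over placebo, and the lowest dose is the one most easily flattered.

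**Working it through.** **1. The plan's own power figure, and whether it uses placebo.** Inputs from the synopsis: 12 per group, SD 0.68, mean changes 0, 0.5, 0.7 and 1.2 at doses 0, 150, 300 and 600 mg. For a least-squares slope, b = Σ(x − x̄)μ / Σ(x − x̄)² and SE(b) = SD / √(n Σ(x − x̄)²).

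- Four groups: x̄ = 262.5 and Σ(x − x̄)² = 196,875. Then b = 375/196,875, or 0.190 g/dL per 100 mg. SE = 0.68/√(12 × 196,875), or 0.0442 per 100 mg. The ratio is 4.31. Simulated power (10,000 repetitions) is 98.6%.
- Three active doses only: x̄ = 350 and Σ(x − x̄)² = 105,000. Then b = 165/105,000, or 0.157 per 100 mg. SE is 0.0606 per 100 mg and the ratio is 2.59. Simulated power is 71.9%.

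The stated lower bound of 85% is met with placebo as dose 0 and missed without it. A drift added equally to all four groups moves the intercept and leaves b unchanged.

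**2. Size of the selection effect.** The protocol gives no Hb distribution, so these inputs are assumptions: true mean 10 to 11 g/dL, between-subject SD 0.8 to 1.0, within-subject SD 0.3 to 0.5. The simulation applies entry at 10.5 or less and one retest of a failing value, and takes the mean of the qualifying and Day 1 values as baseline. The true level exceeds that baseline by 0.03 g/dL on average at the mild end (mean 10, within-subject SD 0.3). At the other end (mean 11, between-subject SD 0.8, within-subject SD 0.5) the excess is 0.18 g/dL.

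**3. Effect on the within-group test.** One-sample t, n = 12, 11 df, non-centrality = drift × √12 / 0.68. For an inactive drug:

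| Common drift (g/dL) | Non-centrality | Rejection per dose |
|---|---|---|
| 0 | 0 | 5.0% |
| 0.03 | 0.15 | 5.2% |
| 0.10 | 0.51 | 7.5% |
| 0.18 | 0.92 | 13.4% |

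**4. What a placebo contrast would deliver.** Two-sample t, 12 against 12, 22 df, non-centrality = δ / (0.68 × √(2/12)):

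| Dose | δ (g/dL) | Non-centrality | Power vs placebo | Power vs baseline |
|---|---|---|---|---|
| 150 mg | 0.5 | 1.80 | 41% | 64% |
| 300 mg | 0.7 | 2.52 | 67% | 90% |
| 600 mg | 1.2 | 4.32 | 98% | >99.9% |

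With the SD pooled over four groups (44 df), the 95% confidence interval half-width for a dose-minus-placebo difference is 2.015 × 0.68 × √(2/12) = 0.56 g/dL.

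**The case against.** The strongest reply is that the inference that matters is already controlled. A reader might infer that the placebo arm goes unused. It does not: it is one of the four groups in the primary regression, the stated power depends on it, and it appears in the by-group summaries. That stands, and it limits the point to the dose-level comparison.

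A reader might also infer that the starting dose will be picked from the tests against baseline. No section says so. The objective ties the starting dose to the dose-response relationship, and no decision rule is attached to these tests.

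The gap between 41% and 64% power at 150 mg might be read as bias. It is not. With a placebo change of 0, as the protocol assumes, both tests target the same 0.5 g/dL, and the gap is the added variance of a two-sample difference.

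Nor do the rescreening rules establish a rise in every arm. A rescreened subject repeats all screening procedures and must again have Hb of 10.5 or less. Intravenous iron must end at least 4 weeks before rescreening, and oral iron is to stay constant during the trial. Averaging with Day 1 dilutes regression to the mean. The background section says that anemia becomes more severe as kidney function declines, so natural drift could be downward.

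Finally, Section 11.5 leaves the full set of efficacy outcomes to the SAP, which is not shown and may add placebo contrasts. That would not dispose of the point. The synopsis names a comparator rather than leaving it open, and the sentence would still have to be reconciled.

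**Conclusion.** The point holds for the dose-level comparison only. As written, that comparison is uncontrolled in a trial that has a randomised control, and it cannot show that a given dose has an effect. The likely inflation is modest: about 5% to 13% per dose instead of 5%, from a selection effect of 0.03 to 0.18 g/dL. The upper figure is about a third of the 0.5 g/dL planned at 150 mg (0.18/0.5 = 0.36). Those figures rest on assumed Hb means and SDs and on the protocol's SD of 0.68; other drift could add to the effect or offset it.

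The primary slope test stands. Leaving pre-treatment Hb out of it is a missed gain in precision, not an error, because unadjusted change is unbiased between randomised arms. That no placebo contrast exists can be said only of the visible text: Section 11 of the latest version and the SAP could not be read. The change is worth making, but nothing here undermines the trial's main conclusion.

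**What to change.** Replace the synopsis sentence with:

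> Each vadadustat dose will be compared with placebo (pooled over tablet counts) for change in Hb to Week 6, as an estimated difference with 95% CI from an ANCOVA with treatment and pre-treatment Hb.

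State that placebo enters the primary regression as dose 0, and include pre-treatment Hb there as a covariate. Report change from baseline by group descriptively, without p-values. Bring Section 11 and the SAP into line.

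The cost is wording only, as all the data are already collected. The price is less favourable dose-level results, with low power at 150 and 300 mg (27% and 54% if Dunnett-adjusted). The contrasts should therefore be presented as estimates with intervals, not as pass-or-fail tests. Adjustment recovers some precision. With equal variances before and after treatment and correlation ρ, the ANCOVA variance is (1 + ρ)/2 of the change-score variance, which is 0.70 to 0.85 for an assumed ρ of 0.4 to 0.7.

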### 3 LIST OF ABBREVIATIONS

AE	adverse event
ALT	alanine aminotransferase (SGPT)
AST	aspartate aminotransferase (SGOT)
BUN	blood urea nitrogen
C	Celsius
CBC	complete blood count
CKD	chronic kidney disease
CRF	case report form
CRO	contract research organization
CV	cardiovascular
dL	deciliter
DVT	deep venous thrombosis
ECG	electrocardiogram
EDC	electronic data capture
eGFR	estimated glomerular filtration rate
EOT	end-of-treatment
EPO	erythropoietin
ESA	erythropoiesis-stimulating agent
EU	European Union
F	Fahrenheit
FDA	Food and Drug Administration
g	gram
GCP	Good Clinical Practice
GFR	glomerular filtration rate
Hb	hemoglobin
HIF	hypoxia-inducible factor
HIF-PH	hypoxia-inducible factor prolyl hydroxylase
ICH	International Conference on Harmonisation
IEC	independent ethics committee
INR	international normalized ratio

---

IRB	institutional review board
IV	intravenous
JSN	Japanese Society of Nephrology
KDIGO	Kidney Disease Improving Global Outcomes
kg	kilogram
LDH	lactate dehydrogenase
MedDRA	Medical Dictionary for Regulatory Activities
µM	micromolar
mg	milligram
mL	milliliter
ND-CKD	non-dialysis dependent chronic kidney disease
ng	nanogram
PD	pharmacodynamics(s)
PE	pulmonary embolism
PK	pharmacokinetic(s)
PP	per protocol
PT	prothrombin time
PTT	partial thromboplastin time
RBC	red blood cell
SAE	serious adverse event
SGOT	serum glutamic oxaloacetic transaminase (AST)
SGPT	serum glutamic pyruvic transaminase (ALT)
TIBC	total iron binding capacity
TSAT	transferrin saturation
ULN	upper limit of normal
US	United States
USA	United States of America
VEGF	vascular endothelial growth factor

## 4 BACKGROUND

### 4.1 Proposed Indication of Renal Anemia

Chronic kidney disease (CKD) is defined using the following criteria in accordance with the guidelines from the National Kidney Foundation Kidney Disease Outcomes Quality Initiative ([NKF 2002](#)) and Kidney Disease Improving Global Outcomes ([KDIGO 2012](#)):

- Kidney damage for greater than 3 months, with or without decreased glomerular filtration rate (GFR) (ie, pathologic abnormalities or markers of damage, including abnormalities in composition of the blood or urine, or abnormalities in imaging tests)
- Decreased GFR levels (ie, less than 60 mL/min/1.73 m^2; GFR categories G3a-G5) for greater than 3 months, with or without kidney damage

CKD is a major public health problem worldwide. In Japan, the prevalence of GFR less than 60 mL/min/1.73 m^2 is estimated to be 20% of the adult population ([Iseki 2008](#)). The number of CKD patients in Japan who require dialysis is >300,000 and has been increasing continually over the last 30 years ([Imai 2011](#)).

The prevalence and severity of renal anemia in CKD increases as renal function deteriorates. Anemia generally exists when hemoglobin (Hb) is less than 13 g/dL in men or less than 12 g/dL in women. Three principal factors contribute to the development of anemia as CKD progresses:

- Peritubular fibroblasts, a type of cell in the kidney, are designed to sense the amount of oxygen carried by the blood. These cells secrete erythropoietin (EPO) to adjust the production of red blood cells (RBCs) by the bone marrow and maintain circulating oxygen levels at normal physiologic levels. As kidney disease progresses, the number of peritubular fibroblasts is reduced and EPO secretion is significantly decreased. This decline in EPO leads to a reduction in RBC production.
- On average, the RBCs in CKD patients have a shorter lifespan (approximate lifespan of 70 days) compared with the RBCs in healthy people (approximate lifespan of 90 to 120 days). Such a condition leads to increased RBC production in CKD patients to maintain normal physiologic levels.
- The availability of iron to the bone marrow is impaired. Iron is a required component in the formation of Hb, and is essential for the transport of oxygen to the tissues of the body.

As CKD progresses, the combined effect of decreased RBC production from lower EPO signaling, increased rate of RBC destruction, and reduced iron availability to the bone marrow results in the increased prevalence and severity of anemia.

The main impact of anemia on organ function is reduced oxygen delivery to tissues leading to a constellation of symptoms including fatigue, shortness of breath, and exercise intolerance ([Stauffer 2014](#)). In these patients, compensatory changes occur in cardiac structure and function including an increase in cardiac output and the development of left ventricular hypertrophy and eventually the development of heart failure ([Metivier 2000](#)). Other consequences from anemia in CKD patients include impaired cognitive function, sleep disorders, and depressed immune function which can impact the quality of life in patients ([Iseki 2007](#), [NICE 2011](#)). Overall, anemia contributes to a poorer prognosis in patients with CKD ([Iseki 2007](#), [Nurko 2006](#)).

